Thus, a tDCS effectiveness score is calculated for each participant in the 4mA and 2mA conditions. These tDCS effectiveness scores will then be the dependent variables in a multivariate logistic regression; once for trained items, again for untrained items. The predictors will be the CSF level of a participant, grey matter volumes and skull thickness around the DLPFC, impairment scores (baseline and cognitive severity), and interactive terms representing the sex of the participant. In this manner, we can examine what individual differences predict the tDCS response in people with AD and if these predictors are the same for two and 4mA tDCS while checking for sex differences. We expect more significant levels of CSF, less DLPFC grey matter, thicker skulls, and greater impairment levels will be predictive of more substantial improvement in the 4mA condition. CSF and grey matter values may be less predictive for how well women respond to tDCS as their relatively smaller heads could compensate for increased shunting levels. Finally, a 2 (male AD, female AD) x3 (4mA, 2mA, SHAM) between-subject repeated measures ANOVA will be run for tasks administered in evaluation: MoCA scores, to check for changes in general cognition, as well as for verbal fluency, digit span, and Corsi to check for generalized executive function differences. These analyses are exploratory.

Funding

This study is supported by BrightFocus Foundation, which reviewed the submitted protocol, and awarded funds to [name] [name] towards completing the proposed study.

Risks

The tDCS protocol for this experiment was determined according to the best practices observed in previous research using tDCS stimulation [45]. Furthermore, tDCS is safe, has virtually no side effects,

is technically easy to carry out, and is not uncomfortable to undergo [46,47]. Multiple studies have also reported that the administration of 4 ma tDCS has no more adverse effects than 2 ma tDCS [48]. No incidence of seizure has been recorded, although side effects could include headache, drowsiness, itching sensation, nausea, and, in rare cases, disorientation. In our experiences, the only observed and reported side-effect has been temporary redness post-stimulation where the sponge was placed, as well as the occasionally reported headache.

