If the event were to result in lasting pain and hospitalization, then it would be reported as a ‘Serious Adverse Event’ and full details would be noted to the research ethics board as well as Health Canada. These events would be recorded on the worksheets being used to collect the rest of the data. We must stress, however, that after administering 4 mA tDCS to around 60 participants, for hundreds of tDCS sessions, we have never encountered any such event. Although we have safety protocols in place for any encountered adverse or severe adverse events, we believe such events will fail to occur in the present study.

Confidentiality

A research study file as well as medical records identifying participants will be maintained within [name] lab. Names and identifying information will be replaced with a code, and the information will be kept on file for 10 years after the end of the study. Data collected from participants’ who withdraw from the study will also be kept, unless participants withdraw consent for its use.

Communication and Publication of Research Results

The found results may be presented at research conferences and written up in a manuscript submitted for a publication in a respected science journal. The data will never be used for commercial goals and all participant information will remain confidential. Individual’s participant data will be presented using a code (e.g., Participant 1), which ensures no reader of the data could identify the participant. The results found can also be used to back-up further studies involving 4 mA tDCS because

we will be able to present formal data demonstrating its effectiveness compared to other intensities of stimulation (SHAM, 2mA) in people with Alzheimer's Disease.

REFERENCES:

2. Zortea, M. et al. Transcranial Direct Stimulation to improve the dysfunction of descending pain modulatory system related to opioids in chronic non-cancer pain: An integrative review of neurobiology and meta-analysis. *Frontiers in Neuroscience*. 2019. 13(128)
3. [name], C., et al. tDCS stimulation alongside picture training improves naming scores in anomic dementia patients. in *Alzheimer's Association International Conference*. 2015. Washington.

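### The protocol's only criterion for a serious adverse event joins two conditions with 'and', so read as the working definition it leaves out hospitalization without lasting pain

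*Protocol*

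**What the plan says.** Four statements in the protocol's Risks section bear on this.

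- **Harms considered.** "No incidence of seizure has been recorded, although side effects could include headache, drowsiness, itching sensation, nausea, and, in rare cases, disorientation". The section adds that the team itself has seen only temporary redness under the sponge and an occasional headache.
- **Trigger and consequence.** The condition for classing an event as serious is worded "If the event were to result in lasting pain and hospitalization". What follows from that classification is that "full details would be noted to the research ethics board as well as Health Canada".
- **Recording.** "These events would be recorded on the worksheets being used to collect the rest of the data".
- **Other procedures.** "Although we have safety protocols in place for any encountered adverse or severe adverse events", the team expects none to occur. The content of these procedures is not given.

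No other part of the protocol defines a serious adverse event or gives a further criterion for one.

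**The concern.** The trigger asks for two things at once, and one of them is pain. Much of what the section discusses need not be painful: seizure, disorientation, drowsiness and nausea. If one of these put a participant in hospital without lasting pain, the event would not match the only description of a serious event that the protocol offers.

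What is at stake is the clarity of safety reporting. Classification as serious is what sends an event to the ethics board and the regulator, so the wording of this sentence matters more than that of the general remarks around it. It also affects how a safety statement can be read. The section reports that no event of this sort was met in around 60 people previously given 4 mA. Taken literally, that refers back to the two-condition event. The Purpose of the Research section hopes that 4 mA may become the convention, so readers will want to know what a statement of no serious events covers.

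**Working it through.** No arithmetic applies. The check is to read the rule as written, apply it to plausible events, and look for other text that would bring in the events it misses.

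**Step 1: the rule.** Taken as the definition, an event is serious when (a) it results in lasting pain and (b) it results in hospitalization.

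**Step 2: the rule applied.**

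| Event | (a) | (b) | Meets the stated trigger? |
|---|---|---|---|
| Severe persistent headache leading to admission | yes | yes | yes |
| Disorientation leading to admission, no lasting pain | no | yes | no |
| Seizure leading to admission, no lasting pain | no | yes | no |
| Lasting pain, no admission | yes | no | no |
| Lasting harm other than pain, no admission | no | no | no |

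The second and third rows matter most. Disorientation is on the section's own list of possible side effects. Seizure is discussed there ("No incidence of seizure has been recorded"), and the Sample section requires that participants have no family history of epilepsy, so the protocol treats it as relevant.

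**Step 3: other text that might bring these events in.**

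- The Sample, Training Sessions and Planned Analyses sections contain no seriousness criterion. Training Sessions says only that someone stays with the participant for safety.
- The sentence on worksheets speaks of 'these events'. It directly follows the sentence on serious events, so it could mean those alone or all adverse events. The text does not settle which.
- The sentence on safety protocols shows that something further exists, but not what it says. It also uses 'severe' where the trigger uses 'serious'. Severity is the intensity of an event and seriousness is its outcome, so the two words are not interchangeable in a reporting rule.

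**Step 4: what changing the conjunction does.** With 'or', the second, third and fourth rows meet the trigger. The fifth still does not, because it has neither feature. The change of one word is therefore necessary but not sufficient, and the sentence must also be matched to the criteria in the safety protocols and the applicable requirements.

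**The case against.** The strongest reply is logical. An 'if' sentence gives a sufficient condition. It does not say that other hospitalizations or seizures go unreported, and the same paragraph says that procedures exist for any adverse event. Both points are correct, and they limit the finding. A reader might infer that a hospitalization, seizure or death without lasting pain would not be reported in this trial, or that serious harm will be under-reported. The protocol does not support that. It contains no 'only if', and the procedures it refers to may hold a wider definition. What stands is that this is the only criterion the protocol states, so anyone working from it alone would take it as the definition.

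A second reply is that 'the event' has no clear antecedent. The preceding paragraph ends on redness and headache, so the sentence may describe a headache that worsens and not define seriousness in general. That reading is possible, and text may have been lost in reading the PDF. If it is right, the protocol has no general seriousness criterion at all, and the sentence still needs clarifying.

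A third reply is that such detail belongs in the statistical analysis plan. The rule for reporting to an ethics board and a regulator is not normally left to that document. Here the rule is also stated, not omitted.

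It is also fair to say that the team's own experience is benign, with headache, a painful event, among the few effects seen. That bears on how often the gap would matter, not on whether the sentence is well drafted.

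**Conclusion.** The point holds as a badly worded rule in the protocol. The only stated trigger for serious adverse event reporting joins lasting pain to hospitalization. Taken as the working definition, it excludes hospitalization without lasting pain and lasting harm without hospitalization, including possible outcomes of harms that the section itself raises.

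This rests on two assumptions: that the sentence serves as the definition because nothing else in the protocol does, and that the safety protocols, which are not shown, are not already quoted elsewhere as the governing text. If those protocols are wider, the Risks section is at odds with them and should be aligned. The conclusion concerns the written rule and not staff conduct.

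The size cannot be given as a number. The protocol offers no rate for such events, and the finding depends on none. The primary comparison of stimulation intensities and the other planned analyses are unaffected. The change is worth making because it concerns participant safety and costs very little.

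**What to change.** In the Risks section:

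1. Replace 'and' with 'or' in the trigger, so that lasting pain and hospitalization are not jointly required.
2. Reconcile the sentence with the seriousness criteria in the safety protocols it mentions and with the applicable reporting requirements, and either state those criteria or refer to the document that holds them. This step is needed because 'or' alone still leaves out lasting harm other than pain that does not lead to hospitalization.
3. Say what 'the event' refers to, and use 'serious' consistently in place of 'severe'.
4. State that the events recorded on the worksheets are all adverse events, not only those classed as serious.

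The cost is a short rewording of one paragraph and, if the worksheets do not already allow for it, a line on them. The downside is possibly a few more reports to file. Sample size, design and analysis do not change.
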